## 3.3 Definition of Baseline values

Baseline will be the last available value prior to the first administration of IMP. Scheduled or unscheduled measurements can be used as the Baseline value. Measurement-specific Baseline definitions (based on the schedule of assessments in the protocol) are presented in [Table 3-1](#).

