**Table 3-1: Definition of Baseline**

Category	Measurement	Definition of Baseline
Efficacy	BASDAI	Visit 2 (Week 0); Screening result if missing at Week 0
	PGADA	Visit 2 (Week 0)

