### **4.2 Handling of dropouts or missing data**

#### **4.2.1 Efficacy data**

##### **4.2.1.1 ASDAS derivation**

If 1 component for the ASDAS is missing at a given visit, and the visit prior to the visit with the missing component data is not the Baseline or Screening visit, the following will apply: the missing component will be imputed by carrying the last observation for the given component forward, and the ASDAS will be calculated accordingly.

If no value is available for that component before the missing visit, or if the visit prior to the visit with the missing component data is either the Baseline or Screening visit, then the next observation will be carried backwards, and the ASDAS will be calculated accordingly.

If an unscheduled or repeat visit with non-missing data for the given ASDAS component is available and this visit is closer to the scheduled visit where the component data is missing, then the component data from the unscheduled/repeat visit will be used in the derivation of the ASDAS score.

If more than one component for the ASDAS is missing, ASDAS will not be calculated and treated as missing.

Any measurements of hs-CRP that are below 2 mg/L will be imputed with a fixed value of 2 mg/L for the purpose of deriving the ASDAS.

The statistical analysis will be performed based on the resulting derived values of ASDAS.

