#### **8.1.1.4 Calculation of Ankylosing Spondylitis Disease Activity Score**

Each of the individual component assessments described above in [Section 8.1.1.1](#), [Section 8.1.1.2](#) and [Section 8.1.1.3](#) are multiplied by a validated factor (van der Heijde et al, 2005) as listed below:

- 0.121 x Total spinal pain (BASDAI Question 2 result)
- 0.058 x Duration of morning stiffness (BASDAI Question 6 result)
- 0.110 x PGADA
- 0.073 x Peripheral pain/swelling (BASDAI Question 3 result)
- 0.579 x (natural logarithm of the hs-CRP [mg/L] + 1)

The results of these individual calculations or weighted components are then summed to obtain the ASDAS.

Handling of missing data and values of hs-CRP that are below 2 mg/L will be handled as described in [Section 4.2.1.1](#).

ASDAS will be calculated at Baseline and at each post-Baseline visit per the schedule of assessments in the protocol.

The primary efficacy analysis will be based on the change from Baseline in ASDAS at Week 12.

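### SAP 4.2.1.1 does not exempt Baseline from its backward-carry rule, so a Week 0 PGADA that alone is missing is filled with a post-dose Week 2 value

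*SAP*

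**What the plan says.** The imputation rule (SAP 4.2.1.1):

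- It opens with "If 1 component for the ASDAS is missing at a given visit" and names no visit to which it does not apply. Its default is to carry the last value forward.
- It switches to carrying the next value backward in two situations. The first is "If no value is available for that component before the missing visit"; the second reads "or if the visit prior to the visit with the missing component data is either the Baseline or Screening visit, then the next observation".
- An unscheduled or repeat visit that lies closer to the scheduled visit may supply the value. There is no condition that it precede dosing.
- The rule stops at one component: "If more than one component for the ASDAS is missing, ASDAS will not be calculated and treated as missing".
- On use, it says "The statistical analysis will be performed based on the resulting derived values of ASDAS".

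The reach of the rule (SAP 8.1.1.4): "ASDAS will be calculated at Baseline and at each post-Baseline visit per the schedule of assessments in the protocol". The same section refers missing data to 4.2.1.1.

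The definition of Baseline:

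- SAP 3.3: "Baseline will be the last available value prior to the first administration of IMP".
- SAP Table 3-1, for both BASDAI and hs-CRP: "Visit 2 (Week 0); Screening result if missing at Week 0". For PGADA it gives Week 0 only.
- SAP 6.3 computes Baseline ASDAS from the Baseline BASDAI, PGADA and hs-CRP and points to Table 3-1 for each.

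The schedule (Protocol Table 5-1 and Section 8.2): PGADA is not assessed at Screening. After Week 0, BASDAI and PGADA are next due at Week 2 and hs-CRP at Week 4. The first dose follows the Week 0 assessments.

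**The concern.** Two rules govern the same input and give different answers. One says that Baseline is pre-dose. The other, taken at its words, can put a post-dose value into the Baseline score. Baseline ASDAS is subtracted in the primary variable and is also the covariate in the Bayesian model (SAP 8.1.2.1), and it fixes who meets the 2.0-unit reduction for ASDAS-MI (SAP 8.2.1.1). A Baseline that already contains some treatment response understates that subject's improvement. If the arms differ in how fast PGADA falls in the first two weeks, the understatement also differs by arm. The programmer or a data evaluation meeting would have to choose between the rules, in a study with three unblinded interim analyses.

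**Working it through.** **The plan's own figure.** SAP 2.4 claims at least 80% power with at least 60 subjects at 2:1 (40/20), difference 0.89, SD 1.17 and correlation 0.35. Reading 1.17 as the SD of raw ASDAS, the adjusted SD is 1.17 x sqrt(1 - 0.35^2) = 1.096. Then 0.89 / (1.096 x sqrt(1/20 + 1/40)) = 2.97, and power at two-sided 5% is 84.3% (normal) or 83.0% (noncentral t). The claim is supported, and the imputation rule does not alter it. The 0.89 serves below only as a scale for group-level effects.

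**Does the rule reach Baseline?** The only scheduled visit directly after Screening is Baseline, so the Screening branch describes a component missing at Baseline. SAP 8.1.1.4 sends Baseline ASDAS to the rule. By contrast, the neighbouring ASAS rule for carrying a value forward (SAP 4.2.1.4) is expressly about post-Baseline visits.

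**Component by component, one component missing at Week 0:**

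| Component | Table 3-1 | 4.2.1.1 as worded |
|---|---|---|
| BASDAI Q2, Q3 or Q6 | Screening value | Week 2 value, after one dose |
| hs-CRP | Screening value | Week 4 value, after two doses |
| PGADA | no fallback | Week 2 value, after one dose |

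For the first two rows the outcome depends on which rule is applied first. For PGADA, Table 3-1 leaves the gap open. With no unscheduled or repeat value to hand, the backward carry is triggered on any order, against SAP 3.3.

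**Size for one subject.** The PGADA weight is 0.110, so a fall of k points by Week 2 makes Baseline ASDAS too low by e = 0.110 x k. For k = 1, 3 and 5 (assumed), e = 0.11, 0.33 and 0.55.

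**After Baseline adjustment.** If Baseline is recorded too low by e, the recorded change (Week 12 minus Baseline) is too high by e. With the historical slope of -0.66 (SAP 8.1.2.2), the model's predicted change also rises by 0.66e. What remains is e - 0.66e = 0.34e; for e = 0.33 this is 0.11.

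**ASDAS-MI.** The tabulated classification takes the whole error. A true reduction of 2.3 with e = 0.33 is recorded as 1.97 and misses the 2.0 cut-off.

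**Group level (simulation).** Assumptions: 40/20 subjects, raw SD 1.17, correlation 0.35, true difference 0.89 and 4000 runs per setting. The error is 0.33 on bimekizumab and 0.22 on CZP (PGADA falls of 3 and 2 points) in an assumed share of subjects.

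| Share affected (of 60) | Prior on CZP mean | Fall in estimated difference | Fall in probability of success, points |
|---|---|---|---|
| 2% (1.2) | SAP | 0.0035 | 0.13 |
| 5% (3) | SAP | 0.0085 | 0.16 |
| 10% (6) | SAP | 0.0171 | 0.73 |
| 2% (1.2) | vague | 0.0008 | 0.08 |
| 5% (3) | vague | 0.0020 | 0.20 |
| 10% (6) | vague | 0.0036 | 0.30 |

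The shift is larger under the SAP prior because that prior holds the CZP mean near -1.78. An upward shift common to both arms then does not fully cancel in the difference.

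**The case against.** The best defence is that SAP 6.3 speaks specifically about Baseline ASDAS and builds it from Table 3-1. Once a missing BASDAI or hs-CRP has been taken from Screening, it is no longer missing and 4.2.1.1 is not triggered. This is the more natural reading, and it stands as far as it goes. No sentence states the order, however, and it does nothing for PGADA.

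For PGADA, one can point to the pre-dose limits in SAP 3.3 and 4.3 and in Protocol 15.2, and to the absence of any change to Baseline in SAP 3.9. Together these support leaving Baseline missing. That is a fair inference about intent, so it would be wrong to say that backward carry is the only rule bearing on PGADA. What remains is a conflict between stated rules.

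The reason given in SAP 3.9 for widening the FAS also suggests that the authors expected some Baseline scores to stay missing. But the wider FAS also lets such a subject in, after which 4.2.1.1 supplies a Baseline. A data evaluation meeting might remove the subject from the PPS, since missing data is a deviation category in SAP 3.4. The criteria sit in a separate document, so this is a possible safeguard and not a stated one.

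The trigger is also narrow. A wholly missed BASDAI removes three ASDAS components, and the score is then missing.

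A reader might go further and infer a large hs-CRP error. For an assumed fall from 15 to 3 mg/L it would be 0.579 x (ln 16 - ln 4) = 0.80, or 0.34 x 0.80 = 0.27 after adjustment. That holds only if 4.2.1.1 overrides Table 3-1, which SAP 6.3 speaks against. The largest simulated effects (a fall of 0.046 in the difference and about 2 points in the probability of success) assume errors of 0.9 and 0.6 in 10% of subjects. Through PGADA, 0.9 would need a fall of 0.9 / 0.110 = 8.2 points.

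**Conclusion.** The point holds in a limited form. As written, SAP 4.2.1.1 fills a Week 0 PGADA that alone is missing with a post-dose value, contrary to SAP 3.3. For BASDAI items and hs-CRP its wording conflicts with Table 3-1, with the order implied but not stated.

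The size is 0.11 ASDAS per PGADA point of early change in each affected subject, of which about a third survives covariate adjustment. The assumptions are the early PGADA fall, the historical slope of -0.66 and the share affected. The documents give no missing rate. PGADA is collected in clinic before dosing, so the number is probably low and the effect on the primary result likely small.

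A reader might infer that the primary comparison is materially contaminated, or tilted toward bimekizumab. The documents support neither. A per-subject error should not be set against the 0.89 group target, and the error differs by arm only if early response differs, which the documents do not show. If bimekizumab did act faster, the shift would be toward no difference.

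**What to change.** Add to SAP 4.2.1.1:

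- The forward and backward carrying rules, and the rule that takes the closest unscheduled or repeat visit, apply to post-Baseline visits only.
- Components of Baseline ASDAS use pre-dose values only, following Table 3-1 and including pre-dose unscheduled values. A missing BASDAI item or hs-CRP therefore comes from Screening.
- If PGADA has no pre-dose value, Baseline ASDAS is missing for the primary analysis.

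The cost is a few lines of SAP text, settled before unblinding. The small downside is that a subject with no pre-dose PGADA leaves the primary analysis instead of entering it with a post-dose Baseline. Planned sample size and power do not change.

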##### **4.2.1.2 hs-CRP**

Any measurements of hs-CRP that are below the limit of quantification (BLQ) will be imputed with the midpoint between zero and the lower limit of quantification (LLOQ) for the purpose of the calculation of summary statistics and changes from Baseline. Measurements for hs-CRP that are above the upper limit of quantification (ALQ), if applicable, will be imputed to the upper quantification limit.

##### **4.2.1.3 ASDAS component data**

Except for the descriptive statistics of hs-CRP as described above, no imputation of missing data will be performed for the summaries of the ASDAS component efficacy variables.

#### **4.2.1.4 ASAS20, ASAS40 and ASAS-PR**

For all non-missed visits, in the calculation of ASAS20, ASAS40 and ASAS-PR responses, if any of the component data are missing, then the following rules will be applied:

- If all the component values are missing from Baseline to the post-Baseline visit being considered, the percentage change from Baseline to that visit for the given component will be imputed as 0%. The unit improvement will be imputed as 0.
- If the component value at a given post-Baseline visit is missing and the Baseline value is present, the missing component will be replaced by the last non-missing post-Baseline observation (LOCF) for that component.

#### **4.2.1.5 BASFI data**

In case of missing answers to 1 or 2 of the single items within the BASFI questionnaire, the BASFI score will be calculated by imputing missing items with the mean of the completed items. Then, the BASFI score will be calculated as described in [Section 8.3.3.1](#). If more than 2 of the items are missing, the BASFI score will be left missing.

#### **4.2.1.6 HADS data**

Any missing data for the total score for HADS-A and HADS-D will be handled as follows:

- If a maximum of 1 item is missing in HADS-A or HADS-D, the missing item will be imputed with the mean score from the remaining completed items within the HADS-A or HADS-D respectively.
- If more than 1 item is missing in HADS-A or HADS-D, the total score will not be calculated.

#### **4.2.1.7 Spinal pain and PhGADA data**

Missing data for Total and nocturnal spinal pain NRS and PhGADA data will not be imputed and will be analyzed as far as data are available.

### **4.2.2 Pharmacodynamic data**

For the PD data, measurements that are BLQ will be imputed with half of the LLOQ for the purpose of calculating summary statistics and changes from Baseline. Measurements that are ALQ, if applicable, will be imputed to the upper quantification limit.

### **4.2.3 Safety laboratory data**

The rules for handling values that are BLQ or ALQ in the safety laboratory data will be the same as those described for PD data in [Section 4.2.2](#).

### **4.2.4 Pharmacokinetic data**

Concentrations that are BLQ will be imputed with half of the LLOQ for the respective analyte (BKZ or CZP) for the purpose of calculating the geometric mean and its 95% CI, the geoCV, the arithmetic mean and SD for summaries and figures.

For the individual figures, any concentrations that are BLQ will be regarded as missing, with the exception of pre-dose BLQ concentrations at Visit 2 (Week 0), which will be imputed with zero for linear scale plots.

#### 4.2.5 Dates and times

Partial dates may be imputed for the following reasons:

- Classification of AEs as treatment-emergent
- Classification of medications as prior or concomitant

Imputed dates will not be shown in the listings; all dates will be displayed as reported in the database.

The following rules will be applied for partial start dates:

- If only the month and year are specified and the month and year of the first dose of IMP is not the same as the month and year of the start date then the 1st of the month will be used, or the date of Screening if this is later (if the latter imputation results in an end date that is earlier than the start date, then the 1st of the month will be used). If time is missing this will be imputed as 00:00 h
- If only the month and year are specified and the month and year of the first dose of IMP is the same as the month and year of the start date, then the date of the first dose of IMP will be used. If this results in an imputed start date that is after the specified end date, then the 1st of the month will be used, or the date of Screening if this is later (if the latter imputation results in an end date that is earlier than the start date, then the 1st of the month will be used). If the imputed date is the same as the date of the first dose of IMP then time will be imputed as the start time of the first injection (ie, an AE will be regarded as treatment-emergent and a medication will be classified as concomitant)
- If only the year is specified, and the year of the first dose of IMP is not the same as the year of the start date then January 01 of the year of the start date will be used. If time is missing this will be imputed as 00:00 h
- If only the year is specified, and the year of the first dose of IMP is the same as the year of the start date, then the date of the first dose of IMP will be used. If this results in an imputed start date that is after the specified end date, then January 01 of the year of the start date will be used, or the date of Screening if this is later (if the latter imputation results in an end date that is earlier than the start date, then January 01 will be used). If the imputed date is the same as the date of the first dose of IMP then time will be imputed as the start time of the injection (ie, an AE will be regarded as treatment-emergent and a medication will be classified as concomitant)

The following rules will be applied to partial stop dates:

- If only the month and year are specified, then the last day of the month will be used
- If only the year is specified, then December 31 of the known year will be used
- If the stop date is completely unknown, the stop date will not be imputed

Missing or partially missing dates and/or times will be imputed as described in [Table 4-1](#) for the calculation of duration of each AE. AE duration will be computed in and reported in day and time format: xx d hh:mm.

**Table 4–1: Calculation rules for duration of adverse events**

Data availability	Onset date/time	Outcome date/time	Calculation rules
Complete data	D1/T1	D2/T2	Duration = $[(D2 - D1) * 24 + (T2 - T1)] / 24 \text{ d}$
End time missing	D1/T1	D2/--	End time is substituted by time 23:59h (=23.98 in decimal format) Duration = $<[(D2 - D1) * 24 + (23.98 - T1)] / 24 \text{ d}$
Start time missing	D1/--	D2/T2	Onset time is substituted by time 00:00h Duration = $<[(D2 - D1) * 24 + T2] / 24 \text{ d}$
Start and end time missing	D1/--	D2/--	Duration = $<D2 - D1 + 1$
Start day and time missing	--/--	D2/T2	Duration = $[(D2 - D0) * 24 + (T2 - T0)] / 24 \text{ d}$ For a subject in the SS, D0 and T0 are the date and time of first administration of IMP and for screen failures, D0 is the date of the Screening visit and T0 = 00:00h
End day and time missing	D1/T1	--/--	If the stop date is missing, duration will not be calculated.
Start and end date missing	--/--	--/--	If the stop date is missing, duration will not be calculated.

### 4.3 Handling of repeated and unscheduled measurements

All repeated and unscheduled measurements will be presented in the data listings, where applicable. The following general rules will apply to all repeated and unscheduled measurements:

- For repeated measurements obtained prior to the first dose of IMP the latest value (which may be scheduled or unscheduled) will be used in the calculation of the descriptive statistics
- For repeated measurements obtained at the designated Baseline visit, the latest value (which may be scheduled or unscheduled) will be defined as the Baseline provided that this occurred prior to the first dose of IMP
- For repeated measurements obtained at any time point after the first dose of IMP, the values will not be included in the calculation of descriptive statistics or changes from Baseline.
- Unscheduled measurements performed for the Early Withdrawal (EW) visit will be assigned to the appropriate visit (Section 4.4) and analyzed accordingly

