Table 12–3 summarizes the approach to investigate PDILI.

This document cannot be used to support any marketing authorization application and any extensions or variations thereof.

PUBLIC COPY

Table 12–3: Required investigations and follow-up for PDILI

Laboratory value		Symptoms ^a of hepatitis or hypersensitivity	Immediate		Follow up	
ALT or AST	Total bilirubin		Consultation requirements	Actions	Testing	Evaluation
≥3xULN	≥2xULN ^b	NA	Hepatology consult. ^c Medical Monitor must be notified within 24 hours (eg, by laboratory alert) and subject discussed with Medical Monitor ASAP.	Immediate IMP discontinuation ^d .	Essential: Must have repeat liver chemistry values and additional testing completed ASAP (see Section 12.6.1.3); recommended to occur at the site with HCP.	Monitoring of liver chemistry values at least twice per week until values normalize, stabilize, or return to within baseline values. ^e
≥3xULN	NA	Yes				
≥5xULN	NA	NA	Need for hepatology consult to be discussed. (required if ALT or AST ≥8xULN). Medical Monitor must be notified within 24 hours (eg, by laboratory alert) and subject discussed with Medical Monitor ASAP.			Monitoring of liver chemistry values at least twice per week for 2 weeks. ^e 
• Immediate IMP

Table 12–3: Required investigations and follow-up for PDILI

Laboratory value		Symptoms ^a of hepatitis or hypersensitivity	Immediate		Follow up	
ALT or AST	Total bilirubin		Consultation requirements	Actions	Testing	Evaluation

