### **11.3 Clinical laboratory evaluations**

Laboratory data (chemistry, hematology, and urinalysis) and changes from Baseline (if applicable) for numeric variables will be listed by treatment group and visit. Any laboratory variables that are BLQ or ALQ will be handled as described in [Section 4.2.3](#). Values outside the reference range for the numeric variables will be flagged in the listings and, in addition, will be listed separately. The reference ranges will also be reported in the listings.

Chemistry and hematology variables presented in [Table 11-1](#) will be summarized by treatment group at each visit, for both observed values and changes from Baseline. Figures of mean and mean change from Baseline will be presented by treatment for the absolute neutrophil count (ANC). All treatment groups will be overlaid on the same plot and the plot will include the error bars based on the SD (ie, mean +/-SD).

Laboratory variables will be grouped according to the laboratory function panel and categorized as normal, high or low, if applicable, based on the reference range supplied by the analytical laboratory. For selected variables that are identified in [Table 11-1](#), the change in category from Baseline will be presented in shift tables at all post-Baseline visits.

The number and percentage of subjects with treatment-emergent markedly abnormal (TEMA) values will be tabulated by treatment group and visit. Markedly abnormal laboratory values will generally be defined as those categorized as Grade 3 or Grade 4 as per the Rheumatology Common Toxicity Criteria (RCTC). Communication with the lead author of the RCTC publication has revealed that the reference ranges for absolute lymphocyte counts (ALC) are in error, therefore ALC criteria will follow the ranges defined as per the Common Terminology Criteria for Adverse Events (CTCAE) Version 4.03 (United States Department of Health and Human Services, 2010). Additional laboratory variables (not present in the RCTC publication) will also be categorized as per the CTCAE Version 4.03. The criteria for identifying TEMA values are presented in [Table 14-5](#) and [Table 14-6](#) for hematology and chemistry values respectively.

Laboratory measurements meeting the criteria for TEMA will be listed separately for hematology and chemistry. The listings will include all measurements for any variable with at least one TEMA result for each subject.

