## 11.4 Vital signs, physical findings, and other observations related to safety

### 11.4.1 Vital signs

The following vital signs measurements will be obtained:

- Pulse rate
- Systolic and diastolic blood pressure
- Temperature

A by-subject listing of all vital sign measurements and changes from Baseline will be presented by treatment group and visit. The listing will include a flag for measurements identified as TEMA/potentially clinically significant (PCS) as calculated by the criteria outlined in [Table 14–8](#). Body weight will be included in the listing.

Descriptive statistics will be reported for all vital sign measurements. Observed values and changes from Baseline will be summarized by treatment group for each vital signs variable and visit.

Figures of mean change from Baseline over time will be presented for each variable by treatment group.

The number and percentage of subjects with TEMA/PCS vital sign values will be summarized by treatment group at each visit. The denominator for the percentages will be the number of subjects with a non-missing measurement for the variable at the specific visit.

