#### **11.4.2      ECG**

The following ECG variables will be reported together with the Investigator's interpretation of the ECG profile:

- PR interval
- RR interval
- QRS interval
- QT interval
- Heart rate
- QT corrected for heart rate using Fridericia's formula (QTcF)

Electrocardiogram results will be reported in the by-subject listings. The listing will also include the changes from Baseline and percentage changes from Baseline and will be presented by treatment group and visit.

Observed results, changes and percentage changes from Baseline will be summarized for each ECG variable by treatment group and visit.

The following cut points in QTcF (observed data and change from Baseline) will be summarized categorically by treatment group (number and percentage of subjects) and visit. The denominator for the percentages will be the number of subjects with a non-missing measurement for the variable at the specific visit.

Observed QTcF data:

- <450msec
- $\geq 450$ msec to <480msec
- $\geq 480$ msec to <500msec
- $\geq 500$ msec

Change from Baseline in QTcF:

- <30msec
- $\geq 30$ msec to <60msec
- $\geq 60$ msec

Electrocardiogram findings including the Investigator's interpretation will be listed separately.

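### The by-visit abnormality tables have no any-time row, so a worst safety value found only on a repeat, unscheduled or early-withdrawal test may be missing from the by-arm counts

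*SAP*

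**What the plan says.** SAP 4.3 first promises listings: "All repeated and unscheduled measurements will be presented in the data listings, where applicable". It then sets its scope: "The following general rules will apply to all repeated and unscheduled measurements". Two of its rules concern values after the first dose. One is about summary statistics and change from Baseline: "For repeated measurements obtained at any time point after the first dose of IMP, the values will not be included in the calculation of" either. The other reads "Unscheduled measurements performed for the Early Withdrawal (EW) visit will be assigned to the appropriate visit (Section 4.4) and analyzed accordingly". No rule says what happens to a first, purely unscheduled post-dose value taken outside the EW visit.

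SAP 4.4 maps EW values to a scheduled visit. If the assessment is not collected at that visit, the value is left out of the summary statistics and only listed. The sole exception is anti-drug antibodies.

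The abnormality tables are specified as follows:

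- Laboratory (SAP 11.3): "The number and percentage of subjects with treatment-emergent markedly abnormal (TEMA) values will be tabulated by treatment group and visit".
- Vital signs (SAP 11.4.1): "The number and percentage of subjects with TEMA/PCS vital sign values will be summarized by treatment group at each visit".
- QTcF cut points, observed and change (SAP 11.4.2): "will be summarized categorically by treatment group (number and percentage of subjects) and visit".
- Liver function (SAP 11.3, Table 14-7): subjects counted on an any-post-Baseline-visit basis.

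SAP 3.1 sets the same pattern in general: apart from time to response, tabulations are by treatment group, visit and time point.

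**The concern.** A table of markedly abnormal values should show how many subjects in each arm ever reached a given peak or nadir. Off-schedule samples are often taken because something already looks wrong, and this protocol will generate them. Section 8.14 allows Unscheduled Visits with ECG, vital signs and safety laboratory tests. Section 12.6.1 requires abnormal liver tests to be repeated, and in its most serious categories Table 12-3 asks for "Monitoring of liver chemistry values at least twice per week until values normalize, stabilize, or return to within baseline values".

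If those values have no place in the counts, the tables can understate abnormality incidence in an arm, most of all where extra monitoring found the extreme. The SAP also specifies no number of subjects ever abnormal per arm for non-liver laboratory values, vital signs or QTcF. By contrast, SAP 4.2.1.1 does let unscheduled or repeat data fill a missing ASDAS component, so the plan uses such data for efficacy but has no safety equivalent.

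**Working it through.** The plan states no figure to reproduce. The check is which value reaches which table, followed by an illustration.

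**Tracing a worst value**

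1. *Abnormal at a scheduled visit, milder on repeat.* The scheduled value is counted. Nothing is lost.
2. *Worst value only on a repeat.* SAP 4.3 keeps it out of descriptive statistics and changes from Baseline. The by-visit tables have no row for it, so it is listed only. Criteria that need a change from Baseline are hit most directly: vital-sign PCS (Table 14-8 requires both a value and a change), part of hemoglobin TEMA (Table 14-5) and the QTcF change categories.
3. *Worst value only at an Unscheduled Visit.* The SAP 4.3 lead-in covers it, but no rule admits it to a table. The vital-sign and QTcF percentages use subjects measured at the specific visit, which points to scheduled-visit rows.
4. *Worst value at the EW visit.* It counts only if the mapped visit schedules that assessment. After Week 12, Protocol Table 5-1 has nine visits through Week 48. Hematology and chemistry are drawn at three (Weeks 24, 36, 48) and not at six (Weeks 16, 20, 28, 32, 40, 44). EW laboratory values mapped to any of those six are only listed.
5. *Liver values.* Table 14-7 is not by visit, but the SAP does not say whether an unscheduled sample counts as a visit. The question also affects the combined transaminase and bilirubin criteria, which must be met at one visit.

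**Illustration, laboratory draws from Week 12 to Week 48 only**

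The draws at Weeks 12, 24, 36 and 48 are 12 × 7 = 84 days apart. Assume random onset and an episode of d days, with d below 84. The chance that it spans a scheduled draw is d/84.

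- d = 14: 14/84 = 17%
- d = 28: 28/84 = 33%

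The durations and the random onset are assumptions; the documents give neither. Up to Week 12 the draws are 14 days apart, so a 14-day episode is always caught (14/14 = 100%). The 84-day gap does not apply to vital signs or ECG, which are scheduled at most 28 days apart through Week 48.

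**What one missed subject is worth**

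With 2:1 allocation, 60 subjects give 40 and 20, and 72 give 48 and 24.

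- Bimekizumab: 1/48 = 2.1% to 1/40 = 2.5%
- CZP: 1/24 = 4.2% to 1/20 = 5.0%

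**The case against.** A reader might infer that the worst safety values are never counted. The documents do not support that. Abnormal values at scheduled visits are counted, EW values are counted where the mapped visit schedules the assessment, and liver abnormalities have their own any-visit table. All potential drug-induced liver injury events must be reported as adverse events (Protocol 12.6.1), hepatic events are tabulated, and Hy's Law cases are summarized (SAP 14.5.8).

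Nor does SAP 4.3 expressly bar all off-schedule values from abnormality counts. Its post-dose exclusion names only repeated measurements, and only descriptive statistics and changes from Baseline. Reading it to cover first unscheduled values and category counts is reasonable, but it is an inference. The abnormality tables say visit, not scheduled visit, and the protocol itself uses the term Unscheduled Visit.

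The liver example is also weaker than it looks. Intensive monitoring starts only after a transaminase has reached 3 times the upper limit of normal. If a scheduled draw found that, the subject is already in Table 14-7 and only a higher category could be missed.

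Finally, every value is listed. SAP 11.3 provides separate TEMA listings showing all measurements of an affected variable, vital-sign PCS values are flagged, and the DMC sees unblinded safety data. In a study of 60 to 72 subjects the listings can be read in full.

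All of this stands and limits the point. What remains is that neither listings nor adverse event tables give abnormality incidence by arm, and that the SAP has no clear rule for an off-schedule value.

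**Conclusion.** The point holds in a limited form. For laboratory TEMA, vital-sign PCS and QTcF categories, a worst value seen only on a repeat, at an Unscheduled Visit, or at an EW visit mapped to a visit without that assessment may be missing from the by-arm counts. It will still be listed and may appear as an adverse event. For Table 14-7 the question is open, because the SAP does not say which samples qualify.

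The size of the loss cannot be derived. A reader might take the complements of the illustration, 83% and 67%, as the share of abnormalities lost. They are not. They are the chance that scheduled Week 12 to Week 48 laboratory draws miss an episode of assumed length. A loss from the tables also requires that an off-schedule sample was taken, and the documents give no rate for that. If none was taken, no extra row would recover the episode.

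The arms are small enough that one omitted subject shifts an incidence by about 2% to 5%. The gap is worth closing because the data are already collected, but it does not undermine the safety analysis as a whole.

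**What to change.** Add one sentence to SAP 4.3: for laboratory TEMA, the Table 14-7 liver criteria, vital-sign PCS and QTcF categories, including criteria based on change from Baseline, an any-time post-Baseline row counts each subject once, by the worst value from all scheduled, repeat, unscheduled and EW measurements through the SFU Visit within its window. Keep the by-visit rows on scheduled values.

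The endpoint should be the SFU Visit and not day 140. That visit is due 20 × 7 = 140 days after the last dose with a window of -3 to +7 days (Protocol 8), so a valid SFU value can fall as late as day 147.

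The cost is one SAP sentence and one row per table. Unscheduled laboratory samples should already go to the central laboratory (Protocol 12.6), and SAP 1 provides for amendment before database lock. The downside is that any-time counts depend partly on how often extra tests were done. A table footnote should say so, and the by-visit rows remain as the comparison on equal schedules.
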